3.2 Exclusion Criteria

Patients who will receive study drug who meet any of the following criteria will be excluded from study entry:

1. Patients that have received an **allogeneic transplant**
2. **Prior allogeneic stem cell transplant** or current **therapy with other anti-neoplastic** or investigational agents
3. Best response of progressive disease prior to ASCT
4. Patients with **any autoimmune disease or a history of autoimmune disease.** Patients with vitiligo, type I diabetes mellitus, residual hypothyroidism due to autoimmune condition only requiring hormone replacement, psoriasis not requiring systemic treatment, or conditions not expected to recur in the absence of an external trigger are permitted to enroll.
5. Any condition requiring **systemic treatment with corticosteroids** (>10 mg daily prednisone equivalents) or other immunosuppressive medications within 14 days prior to first dose of study drug. Inhaled steroids and adrenal replacement steroid doses >10 mg daily prednisone equivalents are permitted in the absence of active autoimmune disease.
6. Use of a study drug ≤ 21 days or 5 half-lives (whichever is shorter) prior to the first dose of nivolumab. For study drugs for which 5 half-lives is ≤ 21 days, a minimum of 10 days between termination of the study drug and administration of nivolumab is required.
7. Wide-field radiotherapy (including therapeutic radioisotopes such as strontium 89) administered ≤ 28 days or limited field radiation for palliation ≤ 7 days prior to starting study drug or has not recovered from side effects of such therapy.
8. Major surgical procedures ≤ 28 days of beginning study drug, or minor surgical procedures ≤ 7 days. No waiting required following port-a-cath placement.

CONFIDENTIAL

STUDY DRUG: NIVOLUMAB

SARAH CANNON DEVELOPMENT INNOVATIONS STUDY NUMBER:

BMT 24

FINAL PROTOCOL DATE: 07 FEB 2020

VERSION 7

9. Previously untreated brain metastases. Patients who have received radiation or surgery for brain metastases are eligible if therapy was completed at least 2 weeks prior to study entry and there is no evidence of central nervous system disease progression, mild neurologic symptoms, and no requirement for chronic corticosteroid therapy.
10. Pregnant or lactating
11. Acute or chronic liver, renal, or pancreatic disease.
12. Uncontrolled diabetes mellitus (fasting blood glucose >250 mg/dL).
13. Any of the following cardiac diseases currently or within the last 6 months:
 - Left ventricular ejection fraction (LVEF) <45% as determined by multiple gated acquisition (MUGA) scan or echocardiogram (ECHO)
 - Corrected QT (QTc) interval >480 ms on screening electrocardiogram (ECG)
 - Unstable angina pectoris
 - Congestive heart failure (New York Heart Association (NYHA) \geq Grade 2 [Appendix B])
 - Acute myocardial infarction
 - Conduction abnormality not controlled with pacemaker or medication
 - Significant ventricular or supraventricular arrhythmias (patients with chronic rate-controlled atrial fibrillation in the absence of other cardiac abnormalities are eligible)
 - Valvular disease with significant compromise in cardiac function
14. Inadequately controlled hypertension (i.e., systolic blood pressure [SBP] >180 mmHg or diastolic blood pressure [DBP] >100 mmHg) (patients with values above these levels must have their blood pressure [BP] controlled with medication prior to starting treatment).
15. Serious active infection at the time of treatment, or another serious underlying medical condition that would impair the ability of the patient to receive protocol treatment.
16. Known diagnosis of human immunodeficiency virus, hepatitis B, or hepatitis C. Testing at baseline is not required.
17. Presence of other active cancers, or history of treatment for invasive cancer \leq 5 years. Patients with Stage I cancer who have received definitive local treatment and are considered unlikely to recur are eligible. All patients with previously treated in situ carcinoma (i.e., non-invasive) are eligible, as are patients with history of non-melanoma skin cancer.
18. Psychological, familial, sociological, or geographical conditions that do not permit compliance with the protocol.

CONFIDENTIAL

STUDY DRUG: NIVOLUMAB

SARAH CANNON DEVELOPMENT INNOVATIONS STUDY NUMBER:

FINAL PROTOCOL DATE: 07 FEB 2020

BMT 24

VERSION 7

3.3 **Discontinuation from Study Treatment**

Patients will be discontinued from study treatment for any of the following reasons:

- Disease progression
- Irreversible or intolerable toxicity or abnormal laboratory values thought to be related to drug toxicity
- Conditions requiring therapeutic intervention not permitted by the protocol
- Intercurrent illness (this will be at the Investigator's discretion)
- Inability of the patient to comply with study requirements
- Patient requests to discontinue treatment
- Patient withdraws consent from the study
- Non-compliance/lost to follow-up
- Pregnancy

After discontinuation from protocol treatment, patients must be followed for AEs for 100 days after their last dose of nivolumab. All new AEs occurring during this period must be reported and followed until resolution, unless, in the opinion of the Investigator, these values are not likely to improve, because of the underlying disease. In this case, the Investigator must record his or her reasoning for this decision in the patients' medical records.

All patients who have Grade 3 or 4 laboratory abnormalities (per National Cancer Institute Common Terminology Criteria for Adverse Events [NCI CTCAE] v4.03) at the time of discontinuation must be followed until the laboratory values have returned to Grade 1 or 2, unless it is, in the opinion of the Investigator, not likely that these values are to improve. In this case, the Investigator must record his or her reasoning for making this decision in the patients' medical records.

4. **PATIENT REGISTRATION**

The patient must willingly consent after being informed of the procedures to be followed, experimental nature of the treatment, potential benefits, treatment alternatives, side effects, risks, and discomforts. Institutional Review Board (IRB) approval of this protocol and consent form is required. Eligible patients who wish to participate in the study will be enrolled into the study.

Registration must occur prior to the initiation of protocol therapy. Patients eligible to participate in the study may be enrolled through the Sarah Cannon Development Innovations Central Enrollment Desk. The enrollment desk may be reached by calling [contact]. Registration may be done: 1) via [contact] Monday through Friday, 8:30 a.m. to 4:30 p.m., Central Standard Time, or 2) via email at [contact]. Patient registration will be confirmed via email within 24 hours or by the next business day.

CONFIDENTIAL

STUDY DRUG: NIVOLUMAB

SARAH CANNON DEVELOPMENT INNOVATIONS STUDY NUMBER:

FINAL PROTOCOL DATE: 07 FEB 2020

BMT 24

VERSION 7

5. STUDY DESIGN

This is a Phase II single-arm open-label study of nivolumab as maintenance therapy after autologous stem cell transplantation in patients with HL at risk of relapse or progression.

Patients will receive nivolumab (240 mg IV) every 2 weeks (± 2 days as long as interval between doses is 12-16 days) starting 45-180 days post-transplant for up to a maximum of 6 months of treatment. To compare immune recovery, a control group of 5 patients will receive standard-of-care procedures and treatment both pre- and post-transplant. Response to treatment for patients receiving study drug will be assessed 6 months and 1 year post-transplant using the Recommendations for Initial Evaluation, Staging, and Response Assessment of Hodgkin and Non-Hodgkin Lymphoma: The Lugano Classification (Cheson et al. 2014, see Appendix F).

The planned enrollment for this study is 40 patients: 35 patients receiving study drug and 5 patients will receive standard-of-care procedures and treatment both pre- and post-transplant.

5.1 Treatment Plan

5.1.1 Nivolumab

Nivolumab: 240 mg IV Day 1 of every cycle (every 2 weeks)

5.2 Treatment Duration

Study treatment consists of a maximum of 6 months of treatment. Patients must receive at least 2 cycles of nivolumab to be evaluable for efficacy.

5.3 Concomitant Medications

Patients who receive study drug will be instructed not to take any additional medications during the course of the study without prior consultation with the research team. At each visit, the patient will be asked about any new medications he/she is taking or has taken after the start of the study drug.

5.3.1 Permitted Concomitant Medications

Premedication with anti-emetics is allowed according to standard practice guidelines.

Medications may be administered for maintenance of existing conditions prior to study enrollment or for a new condition that develops while on study, including but not limited to the following:

- Patients are permitted the use of topical, ocular, intra-articular, intranasal, and inhalational corticosteroids (with minimal systemic absorption). Adrenal replacement steroid doses ≤ 10 mg daily prednisone are permitted. A brief (less than 3 weeks) course of corticosteroids for prophylaxis (e.g., contrast dye allergy) or for treatment of non-autoimmune conditions (e.g., delayed-type hypersensitivity reaction caused by a contact allergen) is permitted. Steroid treatment specified as ≤ 16 mg dexamethasone by mouth (PO) daily tapered in ≤ 4 weeks is allowed only for the treatment of brain edema.

Other medications considered necessary for the patient's safety and well-being may be given at the discretion of the Investigator with the exception of those listed in Section 5.3.2.

CONFIDENTIAL

STUDY DRUG: NIVOLUMAB

SARAH CANNON DEVELOPMENT INNOVATIONS STUDY NUMBER:

BMT 24

FINAL PROTOCOL DATE: 07 FEB 2020

VERSION 7

5.3.2 Prohibited Concomitant Medications

The following treatments are prohibited for patients receiving study drug while in this study:

- No other investigational therapy should be given to patients. No anticancer agents other than the study medications should be given to patients. If such agents are required for a patient, then the patient must first be withdrawn from the study.
- Immunosuppressive agents (except to treat a drug-related AE)
- Immunosuppressive doses of systemic corticosteroids (except as stated in Section 5.3.1)

5.4 Correlative Studies

5.4.1 Biomarker Analysis

Mandatory peripheral blood samples will be collected from patients receiving study drug at Cycle 1 Day 1, Cycle 2 Day 1, Cycle 3 Day 1, end of treatment (EOT [6 months]), and 1 year after the first dose of nivolumab for flow cytometric analysis of PD-1 expression of circulating immune cell subsets, including lymphoid (CD4, CD8, Treg, NK, B) and myeloid cells (monocytes, MDSCs), and expression of other checkpoint receptors, such as LAG-3, TIM-3, TIGIT, or agonists such as ICOS, GITR, OX-40. These samples will be labeled with a unique study identifier and subject code in order to maintain patient confidentiality. These samples have no clinical value and will be used for research only. Information on collection, processing, storage and shipment for cells and plasma/serum will be in the laboratory manual.

5.4.2 Immune Recovery versus Control Group

Correlative studies will compare immune recovery for 5 patients undergoing autologous stem cell transplant for HL but not receiving nivolumab (control) with patients receiving nivolumab as maintenance therapy (treatment). All pre- and post-transplant procedures in the control group will be according to standard-of-care as determined by their treating physician. When complete blood count (CBC) and comprehensive metabolic profiling (CMP) panels are collected results will be entered into the electronic case report form (eCRF) as part of the study record. Blood samples in control patients are to be collected at:

- Between days 45-180 after autologous stem cell transplant
- Every 2-4 weeks (± 5 days) while receiving study treatment based on standard-of-care schedule
- At 6 months (± 7 days) from first sample, and
- At 1 year (± 7 days) from first sample.

5.4.3 Handling, Storage and Destruction of Biological Samples

Once testing has been completed, samples will be stored for an additional year beyond study completion. At this time samples will have all identifiers removed and destroyed. Samples will be thawed, decontaminated, solidified, autoclaved, and then placed into the proper biohazard waste container for further disposal.

CONFIDENTIAL

STUDY DRUG: NIVOLUMAB

SARAH CANNON DEVELOPMENT INNOVATIONS STUDY NUMBER:

FINAL PROTOCOL DATE: 07 FEB 2020

BMT 24

VERSION 7

5.4.4 Withdrawal of Informed Consent for Donated Biological Samples

If a patient withdraws consent to the use of mandatory biological samples, then the samples will be disposed of/destroyed, and the action documented. If samples are already analysed, Sarah Cannon Development Innovations is not obliged to destroy the results of this research.

As collection of these biological samples is a mandatory part of the study, the patient may not continue in the study.

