6. DOSE MODIFICATIONS

If toxicity occurs, the toxicity will be graded utilizing the NCI CTCAE v4.03 (https://evs.nci.nih.gov/ftp1/CTCAE/CTCAE_4.03/CTCAE_4.03_2010-06-14_QuickReference_8.5x11.pdf), and appropriate supportive care treatment will be administered to decrease the signs and symptoms thereof.

There will be no dose reduction of nivolumab; however, treatment delays are allowed. If the toxicity does not resolve to NCI CTCAE \leq Grade 1 after 28 days, then the patient should be withdrawn from the study and observed until resolution of the toxicity.

The dose modifications to be used in this study are presented in Table 1.

CONFIDENTIAL

STUDY DRUG: NIVOLUMAB

SARAH CANNON DEVELOPMENT INNOVATIONS STUDY NUMBER:

FINAL PROTOCOL DATE: 07 FEB 2020

BMT 24

VERSION 7

Table 1 **Dose Level Modifications**

Adverse Reaction	Severity*	Dose Modification
Colitis	Grade 2 diarrhea or colitis	Withhold dose ^a
	Grade 3 diarrhea or colitis	Withhold dose ^a
	Grade 4 diarrhea or colitis	Permanently discontinue
Pneumonitis	Grade 2	Withhold dose ^a
	Grade 3 or 4	Permanently discontinue
Hepatitis	AST or ALT >3 and up to 5 × the ULN or total bilirubin >1.5 and up to 3 × the ULN	Withhold dose ^a
	AST or ALT >5 × the ULN or total bilirubin > 3 × the ULN	Permanently discontinue
Hypophysitis	Grade 2 or 3	Withhold dose ^a
	Grade 4	Permanently discontinue
Adrenal Insufficiency	Grade 2	Withhold dose ^a
	Grade 3 or 4	Permanently discontinue
Type 1 Diabetes Mellitus	Grade 3 hyperglycemia	Withhold dose ^a
	Grade 4 hyperglycemia	Permanently discontinue
Nephritis and Renal Dysfunction	Serum creatinine >2.5 and up to 6 × the ULN	Withhold dose ^a
	Serum creatinine >6 × the ULN	Permanently discontinue
Rash	Grade 3	Withhold dose ^a
	Grade 4	Permanently discontinue
Encephalitis	New-onset moderate or severe neurologic signs or symptoms	Withhold dose ^a
	Immune-mediated encephalitis	Permanently discontinue
Other	Other Grade 3 adverse reaction First occurrence	Withhold dose ^a
	Recurrence of same Grade 3 adverse reactions	Permanently discontinue
	Life-threatening or Grade 4 adverse reaction	Permanently discontinue
	Requirement for 10 mg per day or greater prednisone or equivalent for more than 12 weeks	Permanently discontinue
	Persistent Grade 2 or 3 adverse reactions lasting 12 weeks or longer	Permanently discontinue

*Toxicity was graded per NCI CTCAE v. 4.03.

^a Resume treatment when adverse reaction returns to Grade 0 or 1.

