7.4 End of Study Treatment

After withdrawal from or completion of protocol treatment, patients must be followed for AEs for 100 calendar days after the last dose of study drug. The following assessments will be performed:

- Physical examination, including measurement of weight and vital signs
- ECOG performance status
- AE assessment
- Concomitant medication review
- CBC, including 3-part differential and platelets
- CMP
- Serum or urine pregnancy test
- Research blood sample for correlative analysis

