7.5 Response Assessment

Patients should have PET-CT scans done per institution standard of care. PET-CT scans are required 1-3 months post-ASCT prior to initiation of therapy, 6 months post-ASCT, and 1 year post-ASCT. If there is prior evidence of bone marrow involvement, patients should also have bone marrow biopsy performed if in CR at these staging visits to document response.

Patients discontinuing therapy early receiving >6 cycles with measurable disease at baseline are recommended to have an EOT PET-CT. Patients ending treatment early need to have a PET-CT at 1 year post-ASCT unless patient progresses or starts a new therapy.

CONFIDENTIAL

STUDY DRUG: NIVOLUMAB

SARAH CANNON DEVELOPMENT INNOVATIONS STUDY NUMBER:

FINAL PROTOCOL DATE: 07 FEB 2020

BMT 24

VERSION 7

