All AEs resulting in discontinuation from the study should be followed until resolution or stabilization. All new AEs occurring during this period must be reported and followed until resolution unless, in the opinion of the Investigator, the AE or laboratory abnormality/ies are not likely to improve because of the underlying disease. In this case, the Investigators must record his or her reasoning for this decision in the patient's medical record.

After 100 days following the completion of protocol-specific treatment or discontinuation, only AEs, SAEs, or deaths assessed by the Investigator as treatment-related are to be reported.

CONFIDENTIAL

STUDY DRUG: NIVOLUMAB

SARAH CANNON DEVELOPMENT INNOVATIONS STUDY NUMBER:

FINAL PROTOCOL DATE: 07 FEB 2020

BMT 24

VERSION 7

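### Two withdrawal rules take dosed patients off the study without saying that AE, scan and survival follow-up continues, and so conflict with the follow-up sections

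*Combined protocol and SAP*

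**What the plan says.** Section 5.4.4 deals with a patient who withdraws consent to use of the mandatory research samples: "As collection of these biological samples is a mandatory part of the study, the patient may not continue in the study". It makes no provision for stopping the samples and keeping the patient under observation. Section 5.4.1 says of the same samples: "These samples have no clinical value and will be used for research only".

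Section 6 deals with toxicity that has not returned to Grade 1 or lower after 28 days: "then the patient should be withdrawn from the study and observed until resolution of the toxicity". Section 5.3.2 likewise requires withdrawal from the study before another anticancer agent is given.

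The follow-up sections are worded differently. Section 3.3 lists toxicity among the reasons for stopping treatment ("Patients will be discontinued from study treatment for any of the following reasons") and then says: "After discontinuation from protocol treatment, patients must be followed for AEs for 100 days after their last dose of nivolumab". Section 7.4 agrees: "After withdrawal from or completion of protocol treatment, patients must be followed for AEs for 100 calendar days". Section 7.5 adds: "Patients ending treatment early need to have a PET-CT at 1 year post-ASCT unless patient progresses or starts a new therapy". Section 7.6 continues follow-up for up to two years after the last dose. Section 11.1.5 adds: "All AEs resulting in discontinuation from the study should be followed until resolution or stabilization".

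Section 10.3 places every patient with one dose in both the FAS and the Safety Population. Section 10.4.2 censors PFS at the last tumor assessment in patients alive without progression, and has no separate rule for withdrawal from the study.

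**The concern.** Stopping treatment, stopping research sampling and leaving the study are three different events, and the protocol does not keep them apart. Safety is the primary objective and PFS the secondary one; the samples serve an exploratory objective. Yet refusal of the samples alone is enough to remove a dosed patient from the study, with nothing said about what is still collected.

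The contrast with Section 13.3.1.1 is telling. A patient who revokes authorization for all health information, a much wider withdrawal, is still to be asked for vital status. A patient who withdraws only sample consent has no stated follow-up in 5.4.4.

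At stake are new AEs up to Day 100, the one-year PET-CT and later follow-up in patients whom the analysis sets still count. The scan matters because Section 9 assesses progression at only two times after transplant, six months and one year. The final analysis in Section 10.5.1 also waits for the 12-month assessment in all enrolled subjects, which a patient removed from the study may not supply. Data not collected at the time may not be recoverable later.

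**Working it through.** **1. The provisions side by side, for a dosed patient**

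| Item | 5.4.4 (sample consent withdrawn) | Section 6 (toxicity unresolved at 28 days) | Follow-up sections |
|---|---|---|---|
| The AE that led to withdrawal | Not addressed | Observed until it resolves | 11.1.5: followed until resolved or stable |
| New AEs to Day 100 | Not addressed | Not addressed | 3.3, 7.4, 11.1.5: required |
| One-year PET-CT | Not addressed | Not addressed | 7.5: required after early end of treatment, except after progression or new therapy |
| Later follow-up | Not addressed | Not addressed | 7.6: up to two years from last dose |

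No section says which provision prevails. The gap is widest in 5.4.4. In Section 6 the causative AE is covered, and the last three rows are not.

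**2. Weight of one patient**

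Input: 35 patients receive nivolumab (Section 5). One patient is 1/35 = 2.9% of the treated group. If m of the 35 have unknown 12-month status, the gap between counting all of them as failures and all as successes is m/35. For m = 2 it is 5.7 points; for m = 4 it is 11.4 points. These values of m are assumptions.

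**3. Why the one-year scan carries weight**

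Treatment may start as late as Day 180 after transplant. The six-month scan falls at about 365/2 = 182.5 days. For a late starter it is close to baseline, so the one-year scan may be the only required scan that informs PFS.

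**4. The plan's power figure, and its sensitivity to loss**

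Inputs from Section 10.2: 12-month PFS 50% against 70%, exponential survival, 18 months' accrual plus 12 months' follow-up, n = 36, two-sided 0.05.

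- Hazards per month: λ0 = −ln(0.5)/12 = 0.0578 and λ1 = −ln(0.7)/12 = 0.0297. The ratio is 0.515.
- P(event) = 1 − (e^(−12λ1) − e^(−30λ1))/(18λ1) = 0.4579, as stated.
- Expected events per patient under the null hazard: v0 = 0.4579/0.5146 = 0.8898. Mean difference per patient: 0.8898 − 0.4579 = 0.4320 (unrounded inputs). The exact variance under the alternative is 0.7567.
- Power = Φ[(√36 × 0.4320 − 1.960 × √0.8898)/√0.7567] = Φ(0.854) = 80.3%, as stated.

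With complete follow-up of the 35 treated patients, the same formula gives 79.2% and 16.0 expected events. Random loss of 5%, 10% or 20% of the 35 by 12 months gives 77.4%, 75.6% or 71.7%, with 15.4, 14.7 or 13.5 events. These loss rates are assumed. The calculation treats loss as unrelated to prognosis, so it shows loss of information and says nothing about bias.

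**The case against.** The strongest reply is that neither rule says follow-up ends. The duties in 3.3, 7.4, 11.1.5 and 11.2 run from the last dose or the end of treatment, whatever the patient's study status. Section 7.5 excuses the one-year scan for two reasons only, and withdrawal under 5.4.4 or Section 6 is neither. Section 11.1.5 plainly expects AE follow-up after a patient leaves the study. The protocol also seems to use *study* loosely for *treatment*: 5.3.2 withdraws from the study a patient who needs another anticancer agent, yet 7.6 has follow-up record the start of such treatment. All of this stands. A reader might infer that the two rules stop AE and PFS follow-up outright; the documents support only an unresolved contradiction.

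The loose usage does not dispose of the point. Section 3.3 lists a request to stop treatment and withdrawal of consent from the study as separate items, and 10.4.1 tabulates withdrawal from treatment and from study. A site has grounds for either reading.

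A reader might also estimate the numbers affected from the discontinuation rates in the background: 9% for nivolumab in Section 1.6 (0.09 × 35 = 3.2) and over 30% for brentuximab vedotin in Section 1.4 (0.30 × 35 = 10.5). Those are discontinuations for toxicity in general, not exits under the 28-day rule, and the higher one belongs to another drug and arose mainly from neuropathy. They do not give a rate here.

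Two further objections stand in part. Making sampling a condition of participation is the sponsor's choice, but that choice does not settle what is collected afterwards from a patient already dosed. And rewording Section 6 as a stop to treatment would write a clinical rule beside Table 1, which has its own 12-week provision for persistent reactions; the remedy must therefore avoid that.

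**Conclusion.** The point holds as a conflict between provisions. Read literally, 5.4.4 and Section 6 are at odds with 3.3, 7.4, 7.5 and 7.6, and sites could resolve the conflict differently. It is clearest for 5.4.4, which mentions no follow-up at all. For Section 6 it is limited to new AEs to Day 100, the scans and long-term follow-up.

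The size is 2.9% of the treated group per patient. The total cannot be given, because the documents state no rate for either kind of exit. The power and range figures rest on assumed losses.

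A reader might infer that such losses make PFS look better than it is. Censoring after toxicity may be informative, but it flatters PFS only if those patients progress sooner than the rest, and nothing in the documents shows that. The supported conclusion is avoidable loss of primary safety data and PFS data, with the direction of any PFS bias unknown. The change should be made because it protects both at almost no cost.

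**What to change.** In 5.4.4, state that when consent to the research samples is withdrawn, sampling stops, and that AE follow-up to 100 days after the last dose, the one-year PET-CT and survival follow-up continue unless the patient also withdraws consent to these. Whether treatment continues is for the sponsor to decide and state.

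Reconcile the withdrawal wording in Section 6 and Section 5.3.2 with 3.3 and 7.4 to 7.6, and say that follow-up of dosed patients continues after such a withdrawal. The exception in 7.5 for progression or new therapy stays as it is. The toxicity trigger should not be altered, and no treatment-stopping rule should be written in.

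The cost is two or three sentences in an amendment and matching consent wording. Samples from patients who refuse further sampling are not recovered under the present rule either.
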